# 7.2.4 Baseline Hepatic Function

Baseline hepatic function will be classified based on the National Cancer Institute Organ Dysfunction Working Group (NCI-ODWG) definition using total bilirubin and aspartate transaminase (AST) values. The last observed bilirubin and AST values collected before the first date of study treatment (including Day 1 assuming lab parameter collected before study treatment on Day 1) will be used as baseline. The following table illustrates the classification of hepatic function:

Table 3. Hepatic Function Group Based on Total bilirubin and AST

Hepatic Function Group	Total Bilirubin (mg/dL)	AST (IU/L)
Normal	≤ ULN	≤ULN
Mild Impairment	$\leq$ ULN > ULN and $\leq$ 1.5 × ULN	> ULN any value
Moderate Impairment	$> 1.5 \times ULN \text{ and } \le 3 \times ULN$	any value
Severe Impairment	> 3 × ULN	any value

Note: ULN are based on reported values from each lab.

#### 7.2.5 DIPSS+ Score at Study Entry

For subjects with missing karyotype information at study entry, the DIPSS+ score at study entry will be calculated by utilizing the DIPSS risk score, platelet count, read blood cell transfusion need collected in EDC form 'DIPSS scoring – Study Entry' according to DIPSS+ scoring system in protocol Table 15 and by assuming these subjects do not have unfavorable karyotype.

## 7.3 Demographics and Baseline Characteristics

FAS will be used for this analysis. Categorical variables will be summarized with the number and percentage of subjects. Continuous variables will be summarized with descriptive statistics (number of non-missing observations, mean, standard deviation, median, minimum, and maximum).

The following categorical demographic and baseline disease characteristics (but not limited to) will be summarized as shown in Table 4:

#### Table 4. Demographic and Baseline Characteristics (Categorical Variables)

#### Categorical variable (possible values)

Age  $(18 - < 65, 65 - < 75, \ge 75)$ 

Gender (Male, Female)

Race (White, Black or African American, Asian, American Indian or Alaska Native, Native Hawaiian or Other Pacific Islander)

Ethnicity (Hispanic or Latino, Not Hispanic or Latino)

Region (US, Japan, Rest of World [ROW])

ECOG performance Status (0,1,2)

[figure not shown]
Baseline Renal Function (Normal, Mild, Moderate, Severe)

Baseline Hepatic Function (Normal, Mild, Moderate, Severe)

Type of MF (Primary MF, Secondary MF)

Prior lines of MF treatment (1,2,3,>3)

Response to prior ruxolitinib at screening (Refractory, Relapsed, Disease progression while on therapy, intolerance, stable disease, PV progressed to MF, ET prolonged to MF, not applicable, Other)

# **Table 4.** Demographic and Baseline Characteristics (Categorical Variables) (Continued)

#### Categorical variable (possible values)

Reason for treatment change at study entry (Splenomegaly, Worsening symptoms, Increased need for transfusions, Anemia, Thrombocytopenia, Increasing WBC, Increasing LDH, Others)

Worsening symptoms as a reason for treatment change at study entry (Fatigue, Altered concentration, Early satiety, Inactivity, Night sweats, Itching, Bone pain, Weight loss, Fevers, Edema, Abdominal discomfort, Others)

Splenomegaly only as a reason for treatment change at study entry (Yes, No)

Worsening symptoms only as a reason for treatment change at study entry (Yes, No)

Worsening labs only as a reason for treatment change at study entry (Yes, No)

At least one worsening labs as a reason for treatment change at study entry (Yes, No)

Splenomegaly and worsening labs as a reason for treatment change at study entry (Yes, No)

Splenomegaly and worsening symptoms as a reason for treatment change at study entry (Yes, No)

Worsening symptoms and worsening labs as a reason for treatment change at study entry (Yes, No)

Splenomegaly, worsening symptoms, and worsening labs as a reason for treatment change at study entry (Yes, No)

Change from nadir in palpable spleen length with prior ruxolitinib/JAK2 inhibitor (< -50%,  $\ge -50\%$  to < -25%,  $\ge -25\%$  to < 0%, 0%, > 0% to < 25%,  $\ge 25\%$  to < 50%,  $\ge 50\%$ )

Transfusion dependence status based on Investigators (Dependent, Independent)

Mutation status at study entry from central review (JAK2, CALR, MPL, other mutation categories if applicable)

Platelet count  $(10^9/L)$  (< 75,  $\geq$  75 to < 100,  $\geq$  100)

Hemoglobin (g/dL) ( $< 8, \ge 8 \text{ to } < 10, \ge 10$ )

Unfavorable karyotype at study entry (Yes, No, Not evaluable)

Dynamic international prognostic scoring system (DIPSS) risk at study entry (Low, Intermediate-1, Intermediate-2, High)

[figure not shown]
DIPSS risk at time of diagnosis (Low, Intermediate-1, Intermediate-2, High, Not evaluable)

DIPSS risk at time of ruxolitinib/Jak-2 inhibitor (Low, Intermediate-1, Intermediate-2, High, Not evaluable)

DIPSS plus risk at study entry (Low, Intermediate-1, Intermediate-2, High, Not evaluable)

Bone Marrow Fibrosis Grade at baseline (MF-0, MF-1, MF-2, MF-3)

Note: Worsening labs for prior treatment change includes increased need for transfusions, anemia, thrombocytopenia, increasing WBC or increasing LDH.

The following continuous baseline disease characteristics will be summarized as shown in Table 5.

Table 5. Demographic and Baseline Characteristics (Continuous Variables)

#### **Continuous Variable**

Age (year)

Body weight (kg)

Body height (cm)

BMI  $(kg/m^2)$ 

Number of prior lines of MF treatments

Number of days from last prior ruxolitinib to study drug start

Time (months) since MF diagnosis

Duration (weeks) of prior ruxolitinib exposure

Spleen length by palpation (cm)

Spleen volume (cm^3)

Hemoglobin (g/dL)

Platelet count (10^9/L)

White blood cell (10^9/L)

[figure not shown]
Neutrophil count (10^9/L)

LDH (U/L)

**Baseline TSS** 

# 7.4 Medical History

Medical history and ongoing conditions, including MF related conditions and symptoms will be summarized and listed. Separate summaries will be presented for ongoing and historical medical conditions. The summaries will be presented by primary system organ class (SOC) and preferred term (PT). Data will be coded using the Medical Dictionary for Regulatory Activities (MedDRA). The actual version of the MedDRA coding dictionary will be noted in the statistical tables and clinical study report. The number and percentage of subjects in each medical history category (by MedDRA system organ class and preferred term) will be summarized. The SOC will be presented in alphabetical order, and the preferred terms will be presented in alphabetical order within each SOC. Subjects

reporting more than one condition/diagnosis will be counted only once in each row (SOC or preferred term).

#### 7.5 Prior and Concomitant Medications

Prior and concomitant medications including prior treatments for MF and preceding treatment for polycythemia vera or essential thrombocythemia prior to developing secondary MF will be summarized by generic name. A prior medication is defined as any medication taken before the first date of study treatment.

A concomitant medication is defined as any medication that started before or after the first date of study treatment and continued to be taken after the first date of study treatment, but not after the last date of study treatment. The number and percentage of subjects taking medications will be summarized by generic drug name based on the World Health Organization (WHO) Drug Dictionary for both prior and concomitant medications.

Subjects who report the use of medications more than one time will be counted only once in the summary of any prior or concomitant medication. Subjects reporting two or more uses of the same medication will be counted only once in the total for the associated generic drug name.

# 8.0 Efficacy Analyses

#### 8.1 General Considerations

The primary analysis population for primary endpoint is the Full Analysis Set. Unless otherwise specified, the secondary efficacy endpoints and exploratory efficacy endpoints will be analyzed in Full Analysis Set.

All efficacy results will be presented by cohort unless stated otherwise. For all analyses, unless otherwise specified, data collected after the cutoff date will be excluded from statistical analysis. All spleen volume related endpoints described in Section 3.0 will be based on the assessments from the central review of the radiographic images by an Independent Review Committee (IRC) as described in the protocol.

abbyie Navitoclax/ABT-263

Navitoclax/ABT-263 M16-109 – Statistical Analysis Plan Version 4.0 – 31 January 2023

All response rates and the corresponding 95% confidence interval (Cl) using the Clopper-Pearson method will be provided.

For the analyses of all time-to-event endpoints, survivorship functions will be estimated using Kaplan-Meier product-limit methodology. If reached, median time-to-event and its 95% CI will be presented.

For the analyses of all continuous endpoints, such as change from baseline in score, the scores will be summarized with baseline mean, visit mean, mean change from baseline, mean percentage change from baseline, standard deviation, and the corresponding 95% CIs.

Baseline measurement related to each efficacy endpoint for analysis has been described in Section 7.0.

[figure not shown]
The post-study treatment refers to Post Study Drug Systemic Therapies for Myelofibrosis, Post Study Drug Radiation Therapy and Post Study Drug Transplant. The disease progression (DP) refers to relapse or progressive disease in the Disease Response Assessment Form.

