# 8.4 Secondary Efficacy Analyses

#### 8.4.1 Secondary Efficacy Endpoints

#### 8.4.1.1 TSS Reduction $\geq$ 50% at Week 24 (TSS50W24)

TSS50W24 rate is defined as the proportion of subjects who achieved at least 50% reduction from baseline in TSS at Week 24. TSS score at Week 24 is defined as the average of the daily scores from a 7-day period closest to Week 24 nominal period. The Week 24 nominal period is from Day 163 to Day 169 for subjects enrolled before protocol amendment 8 and from Day 162 to Day 168 for subjects enrolled after protocol amendment 7. The detail of finding the 7-day period closest to the Week 24 nominal period from MFSAF data is as follows. Also refer to Appendix C for more details.

- 1. Step 1: Search TSS 7-day period data in Week 24 nominal period, Day 162-168 (after protocol amendment 7) or Day 163-169 (prior to protocol amendment 8).
- 2. Step 2: If Step 1 data are not available, extend the Week 24 nominal period in increments of ± 1 day (e.g., for subjects enrolled after protocol Amendment 7: Day 163-169 (+1 day expansion), Day 161-167 (-1 day expansion))
- 3. Repeat step 2 in increments of  $\pm 1$  day until  $\pm 7$  days from Week 24 nominal period if data from previous step are not available
- 4. The final TSS at Week-24 is the average of 7-day period closest to the Week 24 nominal period. The following convention is applied to the situation when a pair of 7-day period data has the same distance to Week 24 nominal period: select the 7-day period data which is before Week 24 nominal period.

[figure not shown]
Daily TSS will be considered as missing if not all responses for 7 items are provided. The worst (highest) daily TSS score will be considered the daily TSS for a day when multiple responses were reported on the same day. At least 4 days of scores in the 7-day period of Week 24 Visit are required to calculate the TSS score for Week 24. If a subject does not have at least 4 days of scores in the 7-day period of Week 24 Visit, the subject will not have a TSS score at Week 24. TSS scores obtained after disease progression or start of post-study treatment will not be included in the analysis.

Primary analysis population for TSS50W24 is Full Analysis Set. Subjects with missing percent change in TSS at Week 24 (e.g., zero TSS at baseline, or missing either baseline or post-baseline) are considered as non-responders of TSS50W24.

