#### 8.5.1.5 Change in MFSAF Score

[figure not shown]
Change in average daily MFSAF score of weekly interval (7-day) for each item and TSS (except for Week 23 and Week 25) from baseline will be summarized according to the scoring approach provided in Appendix C. Data after the start of post-study treatment, disease progression will not be included in the analyses. Change in MFSAF score will be analyzed among subjects who had baseline and post-baseline MFSAF score.

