#### 8.5.2 Main Analyses of Exploratory Efficacy Endpoints

The data will be analyzed per Section 8.1.

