### Appendix C. Patient-Reported Outcome (PRO) Assessments

### **MFSAF Version 4.0**

MFSAF v4.0 is a symptom diary in which patients rate the following seven MF symptoms: fatigue, night sweats, abdominal discomfort, pruritus, pain under the ribs on the left side, early satiety, and bone pain on a daily basis using a scale from 0 (absent) to 10 (worst imaginable). The TSS ranges from 0 to 70 and is calculated by summing up the scores from the following 7 questions. The detailed analysis window will be provided in the SPP.

- How Severe Was Worst Bone Pain
- How Severe Was Worst Fatigue
- How Severe Was Worst Itching (Pruritus)
- How Severe Was Worst Night Sweats
- How Severe Was Worst Abdominal Discomfort
- Worst Feel Fullness After Beginning Eat (early satiety)
- Worst Pain Under Ribs Left Side

For each subject, the score will be calculated at each day of a week, and the weekly score is calculated by averaging the total scores across all available days in the week. It is important to note that, at least 4 days of scores are required to calculate the weekly score. However, for baseline score for subjects enrolled under Amendment 7 or before, at least one day of scores are required.

A total of 15 of 7-day period TSS (Table C-1) can be considered as Week 24 TSS. The final TSS at Week-24 is the average of 7-day period closest to the Week 24 nominal period.

[figure not shown]

Table C-1. Example of Week 24 Window for Subjects Enrolled after Protocol Amendment 7

RX Day	1	2	3	4	5	6	7	8 Week 24 Nominal Period	9	10	11	12	13	14	15
155	X														
156	X	X													
157	X	X	X												
158	X	X	X	X											
159	X	X	X	X	x										
160	X	X	X	X	x	X									
161	X	X	X	X	x	X	X								
162		X	X	X	x	X	X	x							
163			X	X	x	X	X	x	X						
164				X	x	X	X	x	X	X					
165					X	X	X	x	X	X	X				
166						X	X	x	X	X	X	X			
167							X	x	X	X	X	X	X		
168								x	X	X	X	X	X	X	
169									X	X	X	X	X	X	x
170										X	X	X	X	X	x
171											X	X	X	X	x
172												X	X	X	x
173													X	X	x
174														X	x
175															x

Navitoclax/ABT-263 M16-109 – Statistical Analysis Plan Version 4.0 – 31 January 2023

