#### **EORTC QLQ-C30**

HRQoL and symptoms will be assessed with the EORTC-QLQ-C30 version 3 published in 2001. The QLQ-C30 is 30-item subject self-administered questionnaire composed of both multi-item and single-item measures on a four-point scale, with 1 as "not at all" and 4 as "very much." The scoring algorithms for scales will follow the scoring manual, except for the summary score defined below.

[figure not shown]
The EORTC QLQ-C30 Summary Score is calculated by averaging all calculated domain scores excluding scores from the domains of Global Health Status and Financial Difficulties. The summary score will be calculated if all of the required 13-domain scores are available. Symptom scales will be subtracted from 100 before averaging for summary score calculation.

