#### PROMIS Fatigue Short Form (SF) 7a

PROMIS® is a system of highly reliable, precise measures of patient-reported health status for physical, mental, and social well-being. PROMIS instruments measure concepts such as pain, fatigue, physical function, depression, anxiety and social function. Fatigue will be assessed using the PROMIS Fatigue SF 7a that has been developed and validated for use in oncology populations. The PROMIS Fatigue SF 7a is a seven-item questionnaire that assesses the impact and experience of fatigue over the past 7 days. The recommended minimum important difference range is 3-5 points; the lower bound (3) is being used as the minimum important difference in this study. Five response options for

question 1-6 are: 1 = Never, 2 = Rarely, 3 = Sometimes, 4 = Often, and 5 = Always, whereas question 7 has reversed response options.

[figure not shown]
Overall total score for PROMIS Fatigue is derived from raw scores according to the scoring manual of PROMIS Fatigue SF 7a. The symptom sub-domain of the PROMIS Fatigue SF 7a includes items 1-3 and the Impact domain includes items 4-7. The scoring for each sub-domain is calculated as the averaging the raw scores.

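### Mean percentage change does not suit individual MFSAF items: zero baselines drop out, and near-zero baselines can dominate or reverse the figure

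*SAP*

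**What the plan says.** SAP 8.1 opens its rule with "For the analyses of all continuous endpoints, such as change from baseline in score" and requires, besides baseline mean and visit mean, "mean change from baseline, mean percentage change from baseline, standard deviation, and the corresponding 95% CIs". No median is listed. SAP 8.5.2 disposes of the exploratory endpoints in one line: "The data will be analyzed per Section 8.1".

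One of those endpoints, in SAP 8.5.1.5, is "Change in average daily MFSAF score of weekly interval (7-day) for each item and TSS". SAP Appendix C says the seven symptoms are rated "on a daily basis using a scale from 0 (absent) to 10 (worst imaginable". The analysis uses subjects with both a baseline and a post-baseline score, and SAP 8.2 rules out imputation for PRO change.

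Elsewhere the SAP deals with a baseline of zero. SAP 8.4.1.1 counts as non-responders "Subjects with missing percent change in TSS at Week 24 (e.g., zero TSS at baseline" and similar cases. SAP 8.5.1.4 does the same for TSS50 at any week, and SAP 8.5.1.3 requires a palpable spleen length above 0 at baseline. No such rule covers the continuous summaries.

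Protocol 8.3.1 plans percentage change only for spleen volume, with mean, SD, median, minimum and maximum.

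**The concern.** A percentage change divides by the baseline. A subject who does not have a symptom at baseline has a score of 0 and no percentage change, but does have an absolute change. That subject cannot improve. Leaving such subjects out is therefore not neutral: it removes stable and worsening subjects and no improvers.

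Among those left, the measure is lopsided. Improvement stops at -100%, while worsening from a very small baseline can reach thousands of percent. A mean and its confidence interval can then describe one or two subjects.

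Two adjacent columns for the same item would rest on different subjects without saying so, and could point in opposite directions. A reader who takes the percentage as the natural measure of relief could misread an item in either direction.

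**Working it through.** The plan gives no figure on this point, so there is none to reproduce. The check asks whether the rule, followed as written, can mislead, and how often.

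**Can baselines of 0 or near 0 occur?** Protocol inclusion criterion 14 applies only to Cohorts 1b and 3. It asks for two symptoms scored at least 3, or a total of at least 12, on 4 of 7 days. Either route can be met with two items, so up to five of the seven may be 0. Cohorts 1a and 2 have no symptom minimum. Assuming item baselines are built like the TSS baseline, the smallest non-zero seven-day mean is one day scored 1, or 1/7 = 0.14. Subjects enrolled under Amendment 7 or earlier average all available days, so with an assumed 29 diary days it is 1/29.

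**Bounds.** Percentage change = 100 × (post − baseline) / baseline.
- Best case: post = 0 gives -100%.
- 1/7 to 10: 100 × (10 × 7 − 1) = +6,900%.
- 1/29 to 10: 100 × (10 × 29 − 1) = +28,900%.
- Baseline 0: undefined.

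**Example A, improvement shown as worsening (30 subjects).** 24 go from 6 to 3, five stay at 0, one goes from 1/7 to 3.
- Mean change: (24 × (−3) + 0 + 2.857) / 30 = -2.30 points.
- The last subject's percentage: 100 × (3 × 7 − 1) = +2,000%.
- Mean percentage change: (24 × (−50) + 2,000) / 25 = +32%, on 25 subjects.
- The sign turns once that one subject exceeds +1,200%, that is, a final score above 13/7 = 1.86.
- Percentage change of the cohort mean: from (144 + 0.143) / 30 = 4.80 to 75/30 = 2.50, or -48%.

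**Example B, worsening shown as improvement (30 subjects).** 15 go from 4 to 2 and 15 from 0 to 4.
- Mean change: (15 × (−2) + 15 × 4) / 30 = +1.0 point.
- Mean percentage change: -50%, on the 15 with a defined value.

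A smaller case behaves the same way: six subjects go from 0 to 2 and four from 4 to 2. Mean change is (12 − 8)/10 = +0.4; mean percentage change is -50% on four subjects.

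**How often?** The documents give no baseline distribution for any item, so this needs assumptions: 30 or 70 subjects; underlying item mean 2 or 4; 0, 10% or 30% of subjects near zero; a true post-to-baseline ratio of 0.6 or 0.8; and 10% of subjects gaining 1 point. Between 2% and 14% of simulated subjects had a baseline of exactly 0. The table gives, among trials whose mean change showed improvement, the share with a positive mean percentage change. Each range runs over the near-zero share.

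| True ratio | Item mean | n = 30 | n = 70 |
|---|---|---|---|
| 0.6 | 4 | 5% to 17% | 1% to 11% |
| 0.6 | 2 | 13% to 25% | 6% to 18% |
| 0.8 | 4 | 24% to 38% | 21% to 41% |
| 0.8 | 2 | 43% to 46% | 49% to 55% |

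For TSS, with an assumed baseline mean of about 24 and n = 30, the share was at most about 1%.

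**The case against.** The strongest reply is that the sentence setting the rule also requires baseline mean, visit mean and mean change. Anyone reading the whole row sees the absolute result. The endpoints are exploratory, the protocol plans no formal tests, and no decision hangs on the column. All of that stands, and it makes the point small. It does not make the percentage column correct.

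Three stronger readings are tempting, and the documents do not support them.

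- *That all PRO scores share the defect.* PROMIS Fatigue responses are "1 = Never, 2 = Rarely, 3 = Sometimes, 4 = Often, and 5 = Always" (question 7 reversed), so there is no zero baseline and no defect was shown there. For QLQ-C30, "Symptom scales will be subtracted from 100 before averaging for summary score calculation" suggests a 0-100 range, but the scoring manual is not in the documents, so a floor of 0 is an inference. SAP 8.5.1.12 names only the summary score, an average of 13 domains for which a baseline of 0 is implausible. The point reaches QLQ-C30 only if symptom scales are reported singly and scored from 0.
- *That the column would hide new diarrhea.* The 68% in Protocol 3.4 is an any-grade adverse event rate and says nothing about how many subjects start at the floor of a QLQ-C30 item. New diarrhea is also counted in the adverse event tables of SAP 9.2. An illustration can be built by assuming scores of 0/33/67/100, with 75% of subjects at 0, 20% at 33 (of whom 30% improve and 20% worsen one level) and 5% at 67 (40% improve one level). If a share p of the floor subjects worsens one level, mean change is 0.75 × p × 33.3 − 1.33: +11.2 points at p = 50%, +3.7 at 20% and +1.2 at 10%. The last two fall below the protocol's 5-point minimum important difference. The size follows from the assumptions.
- *That the percentage will have the wrong sign.* It can; nothing shows that it will.

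**Conclusion.** The point holds for individual MFSAF items and, conditionally, for QLQ-C30 symptom scales reported singly. Followed as written, the rule drops from the percentage column subjects who can only stay level or worsen, gives that column a different denominator from the mean change, and lets a few small baselines govern it. The exclusion and the asymmetry follow from the scale itself. The frequency of sign reversal does not: about 1% to 55% of simulated trials for items, highest where the true effect is small and item scores are low.

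TSS is little affected, at most about 1%, and the symptom entry criterion protects it further in Cohorts 1b and 3. Spleen volume has no zero baseline, so its percentage change is sound. SVR35W24 is untouched, and TSS50W24 already has its own zero-baseline rule. This is a minor reporting matter.

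**What to change.** Amend SAP 8.1 as follows.

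- **MFSAF items, and any QLQ-C30 symptom scale reported singly:** drop mean percentage change. Report mean absolute change with its 95% CI, median absolute change and n, for all subjects with baseline and post-baseline scores.
- **TSS:** keep percentage change only for subjects with baseline above 0, add the median, and state how many were excluded for a zero baseline.
- **Spleen volume:** leave as Protocol 8.3.1 has it (mean, SD, median, minimum, maximum). Replacing these with median and quartiles alone would depart from the protocol for no gain.
- **PROMIS:** leave unchanged.

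The cost is SAP wording and table shells. No data collection, sample size, or primary or secondary analysis changes. What is lost is a percentage figure for single items.
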